There will not be a required waiting period instituted between informing the potential subject and obtaining written consent, but, if the subject requests, he/she will be given a copy of the consent form for consideration and re-approached at another time to assess his/her desire to participate.

The research staff member will review the informed consent document with the participant, including potential risks and benefits of the study, and assurance that their refusal to be a part of the study, or to withdraw from the study, will not influence their clinical services at UM/JMH. Any questions the patient has will be answered by the study staff member or referred to the PI for further discussion with the patient.

Non-English Speaking Subjects

At the present time, only those comfortable communicating in English will be enrolled in the study, due to the fact that many of the evaluation questionnaires are only available in English or have not been validated for use in non-English speaking persons. Based on our previous studies, we anticipate this only affecting a very small proportion of the potential eligible patients.

28) Process to Document Consent in Writing

The subject's consent to participate in this research study will be documented in writing according to standard UM IRB SOP (HRP-091).

29) Drugs or Devices

The study will make use of two devices, neither of which is an investigational device:

1. TENS 7000 (Roscoe Medical; Ohio). This device is a commercially available device used to deliver transcutaneous electrical nerve stimulation via surface electrodes for the relief of pain. It will be used in accordance with its approved labeling. Based on the FDA 510(k) for this device, the TENS 7000 is “intended for use for (1) Symptomatic relief and management of chronic (long term) intractable pain and (2) adjunctive treatment in the management of post surgical and post traumatic pain problems.”

This research is not intended to be reported to the FDA in support of a new indication and there is no intent to use it to support any other significant change in the labeling of the device.

This research is not intended to support a change in the advertising for the device.

This research does not involve a route of administration, dose, or other factor that significantly increases the risk associated with use of the device.

Storage of the devices and the self-stick electrodes will be in the offices of the research staff (Lynn Rehabilitation Center (rooms 3.153b, 3.154, or 3.156), [name].) when not being used for study subject treatment sessions. These rooms are secured with key cards and have filing cabinets with key locks in which the devices and associated supplies will be kept. When they are removed for use during treatment sessions, they will be in the possession of research study staff. All such devices will be labeled with ownership information, including PI name, research coordinator name, and contact information.

2. Thermo-Sensory Analyzer II (TSA-II; Medoc Ltd.; Israel). This device will be used for the longitudinal assessment of tactile and thermal sensory and pain thresholds. This device is not being tested as an intervention, nor for the purpose of altering labeling or advertising of the device. It is being used as an assessment tool only, and in accordance with all labeling by the manufacturer (Medoc Ltd.). The TSA-II has been used in our lab in multiple studies, and by other labs around the world, for research in human subjects. For the current study, we will use the vibration and

thermal testing apparatus to quantitatively assess tactile, thermal, and pain thresholds in subjects during the full assessment sessions (4 times during the 12-month enrollment). The TSA-II is a precise, computer-controlled device which delivers calibrated thermal stimuli as programmed through the associated software. The device and laptop used to run the equipment are mounted to a mobile cart for easy transport to any location. The TSA-II has been used extensively in human subjects' research, including studies in spinal cord injury patient populations, and the PI has over ten years previous experience using this equipment for the evaluation of somatosensory function in patient groups and control subjects.

Storage of the TSA-II will be in the offices of the research staff (Lynn Rehabilitation Center (rooms 3.153b, 3.154, or 3.156), [name]). These rooms are secured with key cards that are only accessible to research staff, under the supervision of the PI. Access to controlling the device is obtained via the laptop/software program which requires a password to access. The device will be labeled with ownership information, including PI name, research coordinator name, and contact information.

BIBLIOGRAPHY

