Modality	SCI		Nondisabled	
	ICC (95% CI)	# total test sites	ICC (95% CI)	# total test sites
Log MDT	0.84 (0.75-0.90)	56	0.63 (0.45-0.76)	58
Log VDT	0.90 (0.84-0.94)	67	0.86 (0.79-0.91)	80
Log CDT	0.90 (0.83-0.94)	55	0.68 (0.54-0.78)	80
Log WDT	0.95 (0.91-0.97)	50	0.70 (0.57-0.80)	79
CPT	0.50 (0.28-0.67)	56	0.49 (0.31-0.64)	80
HPT	0.50 (0.28-0.66)	62	0.68 (0.55-0.79)	79

MDT = mechanical detection threshold; VDT = vibration detection threshold; CDT = cool detection threshold; WDT = warm detection threshold; CPT = cold pain threshold; HPT = hot pain threshold

severity of chronic neuropathic pain symptoms, in participants with chronic SCI.^{6, 8, 74} **Figure 4** shows that, in test sites in body areas where neuropathic pain symptoms were present, lower pain thresholds (i.e., increased pain sensitivity) were associated with more severe neuropathic pain scores.

Thus, previous work by the study investigators demonstrates that the study is feasible and that they have the skills and tools necessary to perform the proposed study. Results from this body of work support the rationale of the proposed site-specific study.

Figure 4: Pain threshold is negatively related to severity of NeuP in those with SCI

Subjects with SCI and NeuP ($n = 22$) completed sensory testing at sites within the area affected by NeuP. Thresholds were also obtained in control subjects at the same test sites on the body and used to calculate z-scores for the thresholds obtained in those with SCI. Subjects with less loss of pain sensation (z-scores close to 0) had significantly higher NPSI scores than those with greater loss of pain sensation (higher z-scores).⁷⁴ (Z-scores reflect the degree to which thresholds in participants with SCI vary from the distribution of thresholds obtained in nondisabled control subjects, and allow for comparison of measures obtained at different locations on the body.)

4) Inclusion and Exclusion Criteria*

Inclusion criteria:

- Age ≥ 18 ;
- Traumatic spinal cord injury;
- Date of injury occurring within four months of study enrollment.

Exclusion criteria:

- More than four months since date of injury;
- Contraindications for the study intervention, transcutaneous electrical nerve stimulation (TENS),⁸⁸ including:
 - Implanted electronic device such as a pacemaker;
 - Cardiovascular problems;
 - Pregnancy;
 - Epilepsy;
 - Cancer;
- Persons with a spinal cord injury at the C2 level, as placement of TENS electrodes on the neck is not recommended;

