- Cognitive dysfunction which limits the ability of the participant to adequately understand procedures and risks.
- Prisoners

- Pregnant Women

Special populations:

- Adults unable to consent: excluded from study
- Individuals -who are not yet adults: individuals who are less than 18 years old will be excluded from the study
- Pregnant women: Women who are known to be pregnant will not be recruited into the study. A pregnancy test will be administered to females prior to enrollment in TENS (or sham) treatment. Women who become pregnant before or during the 8-week TENS treatment period will be discontinued from the study. Women who become pregnant after the 8-week TENS treatment portion of the study will continue to be enrolled, and followed according to protocol guidelines (no information will be collected specifically on the pregnancy or fetus).
- Prisoners: excluded from study
- Neonates: not applicable

5) Number of Subjects*

This is a single-site study and 98 potential participants with newly-acquired spinal cord injuries will be enrolled. See section 22, for more information.

6) Study-Wide Recruitment Methods*

This is not a multi-center study. See section 21.

7) Study Timelines*

It is anticipated that subjects will be enrolled in the study for 12 months (see **Figure 5**, in section 10, below, for procedures timeline).

It is anticipated that enrollment of subjects will occur between November 1, 2016 and January 1, 2022. This enrollment end date is 12-months prior to the end of the funding cycle for this grant, which will allow for complete follow-up of all subjects before study termination.

The estimated date for the investigators to complete this study is October, 2022.

8) Study Endpoints*

The primary study endpoints/outcomes are: 1.) the percentage of subjects who develop chronic neuropathic pain at the 12-month post-spinal cord injury time point (as defined by a score of ≥ 2 on the Spinal Cord Injury Pain Inventory (SCIPI), a self-report scale of symptoms); and 2.) the severity of chronic neuropathic pain (as measured by a self-report rating of neuropathic pain symptoms) measured at the 12-month post-spinal cord injury time point. The secondary study endpoints/outcomes include other aspects of pain symptoms and physical and emotional function. All outcomes and other variables are listed in Table 2 and described in detail below, within the “Procedures Involved” section.

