Assessments of primary and secondary outcome measures will occur at the time points

diagramed in Figure 5. Details regarding the specific assessment tools and measures to be used are described below and listed in **Table 2**. The primary outcome variables for Aim 1 (Spinal Cord Injury Pain Instrument (SCIPI)⁸⁰ score of ≥ 2 , and Neuropathic Pain Symptom Inventory score⁸⁹) will be collected during each scheduled assessment (full and abbreviated assessments), with additional outcome measures recorded less frequently (during full assessment sessions only: 4 times during the study).

Randomization and blinding procedures:

A blocked randomization procedure will be used, so that for each eight patients enrolled, four will be allocated to TENS and four to Sham TENS. A computer-generated random assignment sequence will only be accessible to the study staff member responsible for delivering TENS treatments. The PI of the study, the researchers evaluating pain diagnoses, and the research subject will not be informed of the treatment allocation assigned. All subjects will be told that they may or may not feel the stimulation from the TENS unit during treatment sessions due to the parameters of the study. The stimulation parameters of the TENS unit will not be visible to the subject, so that subjects will not obviously know to which study group they were randomized.

Treatment procedures:

(a) *TENS device*: The TENS 7000 Dual Channel battery-powered digital stimulator (Roscoe Medical, Ohio, USA) will be used. This device provides for adjustable frequency/pulse rate, pulse width, and amplitude, as well as recording of session data (settings and duration of treatment session). The TENS 7000 device has two channels. Each channel will be connected to two self-stick square electrodes (thus, a total of 4 electrode pads will be used) with dimensions of 2 inches by 2 inches. New electrode pads will be used for each treatment session.

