(a) *Assessment procedures*: **Table 2** lists measures that will be collected during full and abbreviated assessments, as well as before and after each TENS session. Full assessment sessions will occur at three time points: baseline (prior to treatment initiation); termination of the 8-week treatment protocol; and 12 months post-injury. The full assessment protocol will require approximately 180 minutes to complete and may be completed in multiple sessions due to participant availability. An abbreviated assessment protocol will be administered at the 4-week treatment time point (i.e., halfway through the full series of treatment sessions), and over the phone each month after treatment has ended, until the 12-month post-injury time point. The abbreviate assessment will require 30 minutes to complete. In addition, numerical ratings of pain and the Neuropathic Pain Symptom Inventory⁸⁹ will be assessed before and immediately after each 30-minute TENS session. (It is expected that, for most patients, pain ratings will be “0,” as many will not have developed neuropathic pain symptoms in the first few months after injury when TENS is being administered. Collection of this information is important in order to insure that TENS is not related to any increase in pain symptoms during treatment.) Adverse events/ side effects will also be captured at the end of each TENS session. The assessment schedule is depicted by the blue and yellow boxes at the bottom of **Figure 5**.

Table 2: List of assessment tools to be used

Assessment domain	Assessment	Full assessment	Abbreviated assessment	Treatment sessions
Pain classification	SCIP, and ISCPBDS2	X	X	
Pain intensity and symptoms	NRS for pain ISCPBDS2	X	X	X

	ISCIPEDES [“pain symptoms” subset]	X		
	NPSI	X	X	X
	sf-MPQ-2	X		
Maladaptive pain coping	PCS	X		
Sensory function	ASIA sensory scores*	X		
	QST	X		
Emotional function	PHQ-9*	X	X	
	SCI-QOL Resilience scale – short form *	X	X	
Treatments	Frequency, dose, effectiveness (from ISCIPEDES)	X	X	
Adverse events	Incidence and severity			X
Time required (minutes)		120	30	5

* measures/assessments that overlap with national database Form I/II

** assessments that will only be carried out at 12-months post-injury

(b) *Assessment tools:* Copies of all instruments to be used are uploaded within the eProst UM-IRB application for this study.

i. Pain classification:

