Subjects will be withdrawn from the research without their consent if the PI or other study staff, including trained clinicians, determine that the subject may experience adverse events of greater than mild severity and of greater than 10% frequency. If the TENS stimulation is not tolerated after adjustment of electrode location and/or after reduction of stimulus amplitude, then the subject will be withdrawn from the study and will receive no further treatments.

Participants who either self-withdraw from treatment or who are withdrawn by the PI or study staff from the treatment portion of the study, will continue to be followed during all time points after the treatment sessions have terminated, unless the participant does not want to participate in follow-up session for the study.

14) Risks to Subjects*

TENS therapy poses minimal risks to patients, as outlined below.

- a. Skin irritation: Persons undergoing TENS treatment may experience minor skin irritation as a result of the electrode placement.
- b. Painful or unpleasant sensory sensations: TENS may evoke painful or unpleasant sensations for a brief period of time while the appropriate intensity level is being determined.
- c. Emotional upset: Persons with disability may become upset at having questions asked about their disability and the pain conditions associated with their SCI.

Use of the TSA-II device also poses risks:

- d. Thermal pain testing can result in sensations that are unpleasant and which may lead to short-lived, mild-to-moderate anxiety and discomfort. Temporary mild redness around the area tested may occur but will be short-lasting.

To minimize the specific risks outlined above, the following procedures will be in place:

- a. Electrode skin irritation can be reduced by cleaning the skin before electrode placement. The risk of this occurring is low. Electrodes will not be placed near

open wounds. The treatment and control groups will be monitored by the research staff continually throughout each treatment session.

b. The research assistant or other research staff responsible for delivering the TENS treatments will be present during the entire 30 minute treatment session so that if discomfort occurs, the stimulus level can easily be reduced or the TENS electrodes can be removed, and summon one of the study physicians if evaluation is needed.

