Potential participants for this study will be recruited through the JMH inpatient SCI rehabilitation services. All subjects who are at least 18 years of age and who are admitted to the Jackson Rehabilitation Hospital/Lynn Rehabilitation Center with a traumatic spinal cord injury will be assessed for eligibility. Using the inclusion and exclusion criteria provided above, the inpatient SCI rehabilitation physician ([name]) will access Jackson electronic medical record information for this purpose. If the patient meets criteria, the study physician will approach the patient and ask if he/she would agree to have a study team member talk to them about the study for possible enrollment.

All those who agree will be approached in person or over the phone by a research staff member for possible enrollment within 4 months of their injury. Patients who express interest in the study will be informed in detail of the procedures and timeline of the study. The research staff member will then review the informed consent document with the participant, including potential risks and benefits of the study, and assurance that their refusal to be a part of the study, or to withdraw from the study, will not influence their clinical services at UM/JMH. Any questions the patient has will be answered by the study staff member or referred to the PI and/or study physicians for further discussion with the patient. (See section #27 for full consenting procedures.)

Cash and check payments will be made to subjects based on completion of each treatment and assessment portion of the study: 1) \$25 will be paid for each treatment session attended; 2) \$150 will be paid for each full assessment session completed (partial payment, in the amount of \$75, may be paid if the participant completes only the questionnaire portion of this visit, but does not complete the sensory assessment portion); 3) \$25 will be paid for each brief assessment session completed; and 4) a \$50 bonus will be conferred at the end of the study for subjects who complete 90% or more of study treatments, visits, and phone assessments. Up to a total of \$1075 at completion of the study is available for each subject. Cash payments will be given to the subject immediately after each treatment session and in-person assessment session. Check payments may be made via mail for phone assessment if payment in person is not feasible.

22) Local Number of Subjects

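### Pregnancy during the 8-week treatment appears to end a randomised woman's follow-up as well as her stimulation; it should stop treatment only

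*Combined protocol and SAP*

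**What the plan says.** Section 4 (Inclusion and Exclusion Criteria, Special populations) sets two pregnancy rules side by side.

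- Before or during treatment: "Women who become pregnant before or during the 8-week TENS treatment period will be discontinued from the study".
- After treatment: "Women who become pregnant after the 8-week TENS treatment portion of the study will continue to be enrolled, and followed" under the usual protocol schedule.

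The exclusion criteria in the same section place pregnancy in the list headed "Contraindications for the study intervention, transcutaneous electrical nerve stimulation (TENS"). A pregnancy test is given before treatment starts.

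Section 13 (Withdrawal of Subjects) has a general rule. Participants who leave the treatment portion, by their own choice or by decision of the PI or staff, are still followed at all later time points unless they decline. It does not mention pregnancy.

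**The concern.** The primary analysis in section 11 compares the proportions with neuropathic pain at 12 months post-injury. It needs that outcome from every randomised subject, including those who stop treatment early.

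The pregnancy rule appears to take one group out of follow-up for a reason that bears only on treatment. A woman who conceives in week 5 of stimulation would be told that she has left the study, and her 12-month outcome would be missing. A woman who conceives a week after the last session would be followed to the end. The protocol gives no reason for treating the two differently.

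At stake is completeness of follow-up in the randomised groups. Once visits and calls lapse, the outcome may not be recoverable.

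**Working it through.** **1. What the sentence means.** Taken alone, discontinuation from the study could be shorthand for stopping treatment. The sentence that follows narrows this. It says that later pregnancies stay enrolled and are followed, which would be no contrast if the earlier group were also to be followed. The natural reading is that follow-up stops for the earlier group.

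**2. Whether ending follow-up is needed.**

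- *Reason for the rule.* Section 4 lists pregnancy as a contraindication to TENS. That calls for stopping stimulation, not for stopping questions about pain.
- *Nature of the primary outcomes.* Section 8 names the SCIPI score and a self-rating of neuropathic pain symptoms. Section 9 says that the primary outcome variables "will be collected during each scheduled assessment (full and abbreviated assessments").
- *Mode of collection.* Section 9 schedules the abbreviated assessment "over the phone each month after treatment has ended, until the 12-month post-injury time point". The 12-month visit is a full assessment, but section 21 provides for a partial payment that "may be paid if the participant completes only the questionnaire portion of this visit, but does not complete the sensory assessment portion". So a concern about thermal testing in pregnancy would not block the primary outcome.
- *The protocol's own practice.* Section 4 follows women who become pregnant after treatment. Section 13 follows subjects whose treatment is stopped. Section 12 would end the intervention but keep follow-up if TENS proved harmful.

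Nothing in the document requires follow-up to end.

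**3. The plan's own figures (section 11).** Inputs: 98 enrolled, 15% drop-out, 41 completers per arm, 60% v 30%, two-sided alpha 0.05, power of at least 80%.

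- Completers: 98 x 0.85 = 83.3, against about 82 stated.
- Power, pooled variance under the null: mean rate 0.45. Null SE = sqrt(0.45 x 0.55 x 2/41) = 0.110. Alternative SE = sqrt((0.24 + 0.21)/41) = 0.105. Power = Phi[(0.30 - 1.96 x 0.110)/0.105] = 79.0%.
- Power, unpooled variance: Phi[0.30/0.105 - 1.96] = 81.7%.

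The stated design reproduces to rounding.

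**4. How many women.** The protocol gives neither the share of women nor a pregnancy rate. These are assumptions: 10% to 30% women, and 0.5% to 2% risk over 8 weeks.

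- Low end: 98 x 0.10 x 0.005 = 0.05 expected; chance of at least one = 1 - 0.995^9.8 = 5%.
- High end: 98 x 0.30 x 0.02 = 0.6 expected; chance of at least one = 1 - 0.98^29.4 = 45%.

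**5. Scale of one lost outcome, for orientation.** This supposes that the loss is additional to the drop-out allowance.

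| Arm | All 41 | Lost subject had pain | Lost subject had no pain |
|---|---|---|---|
| Sham | 24.6/41 = 60% | 23.6/40 = 59.0% | 24.6/40 = 61.5% |
| TENS | 12.3/41 = 30% | 11.3/40 = 28.25% | 12.3/40 = 30.75% |

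This is the mechanical effect of losing any one subject, not a bias. Pooled-formula power falls from 79.0% to 78.5%.

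**6. Effect of keeping her.** Suppose that a TENS subject who stops early has the sham rate. Keeping her makes the TENS rate (40 x 0.30 + 0.60)/41 = 30.7%, a difference of 29.3 points.

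| Power | Kept (41 v 41) | Lost (40 v 41) |
|---|---|---|
| Pooled formula | 76.9% | 78.5% |
| Exact, same z-test | 79.3% | 77.8% |

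The two methods disagree on direction, because exact power moves in jumps with sample size. Power is therefore no argument for the change.

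**The case against.** **The phrase may have been meant loosely.** Section 13 says of a subject who cannot tolerate stimulation: "then the subject will be withdrawn from the study and will receive no further treatments". The next paragraph of that section then keeps subjects whose treatment is stopped by the PI or staff in follow-up. If study withdrawal there means stopping treatment, the same could be meant in section 4. A pregnancy stop is also a decision by the PI or staff, and section 13 lists no reasons, so its silence on pregnancy proves little. This stands in part and limits confidence to medium. It does not remove the point, because section 4 has its own contrasting sentence and staff would have to guess which rule governs.

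**The impact is close to nil.** A test precedes treatment, the window is 8 weeks, both arms are treated alike, and 41 per arm is already net of drop-out. All of this stands, and it is why the point is minor.

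**A stronger reading that does not hold.** A reader might infer that stops for adverse events or intolerance also end follow-up. Section 13 says "Subjects will be withdrawn from the research without their consent" in the adverse-event case, and section 12 speaks of discontinuing a sensitive subject's participation. Sham is turned down until nothing is delivered, so losses for intolerance would fall almost only on the TENS arm and could bias the comparison. The document does not support this inference. The section 13 follow-up paragraph comes directly after those rules and already covers subjects stopped by the PI or staff. Sections 12 and 13 need no change on this account.

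**Conclusion.** The point holds for pregnancy arising between randomisation and the end of the 8-week treatment. Read with the sentence after it, the section 4 rule ends follow-up and forgoes the 12-month primary outcome without need.

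Severity is minor. Probably no subject or one is affected, on the assumed ranges above. The loss does not depend on arm, no bias is expected, and the 15% drop-out allowance may cover it. A reader might infer a biased comparison or a material loss of power; neither follows.

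Pregnancy found before randomisation is not at issue. Confidence is medium, since the wording may have been intended to mean treatment only.

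**What to change.** Replace the sentence in section 4 with: *Women who become pregnant after randomisation and before the end of the 8-week treatment will stop study treatment and continue to be followed under section 13, unless they decline.* The handling of pregnancy found before randomisation stays as it is.

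**Cost.** One sentence, a few more assessments and some staff time. The section 21 payments imply 7 brief assessments: 1075 - 16 x 25 - 3 x 150 - 50 = 175, and 175/25 = 7. A woman who stops at the start of treatment would have at most 7 x $25 + 2 x $150 = $475 of assessment payments left. Keeping a subject who had little treatment also dilutes the contrast slightly, as shown in the working.
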